11.5. Pharmacokinetic Analyses

PK parameters for each subject will be estimated using non-compartmental analysis (NCA). Descriptive statistics will be provided for all plasma concentration data by analyte/dose/study day/time and for each PK parameter by analyte/dose/study day, as appropriate.

11.6. Safety Analyses

Safety endpoints will include AEs, clinical laboratory measurements, vital sign measurements, ECG recordings, physical examination findings, ECHO/MUGA findings, and ophthalmologic findings. AEs and abnormal laboratory values will be graded according to the NCI-CTCAE version 5.0.

Safety analyses in general will be descriptive and will be presented in tabular format with the appropriate summary statistics. In Dose Escalation, the number of DLTs identified among the DLT-evaluable subjects in the DLT-evaluable set will be listed and summarized by dose level.

11.6.1. Adverse Event Analyses

A TEAE is defined as an AE that emerges during the treatment period (from first DS-1205c/gefitinib dose date until follow-up call [Section 6.1.3.9 or Section 6.2.2.10] after the last dose of study medication), having been absent at pre-treatment; or reemerges during treatment, having been present at baseline, but stopped prior to treatment; or worsens in severity after starting treatment relative to the pre-treatment state, when the AE is continuous.

The number and percentage of subjects reporting TEAEs will be tabulated by the worst NCI-CTCAE Grade, System Organ Class (SOC), and Preferred Term (PT).

Similarly, the number and percentage of subjects reporting treatment-emergent SAEs will be tabulated, as well as TEAEs/SAEs considered related to DS-1205c or gefitinib.

A by-subject AE (including TEAE) data listing will be provided including, but not limited to, verbatim term, PT, SOC, NCI-CTCAE Grade, and relationship to study medications.

Deaths, other SAEs, and other significant AEs, including those leading to permanent discontinuation from study treatment, will be listed.

AESIs will be added as needed. The details will be described in the SAP.

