2.2.2. CCI

2.3. Study Endpoints

2.3.1. Dose Escalation

Primary Endpoints (ie, Primary Outcome Measures)

- To determine the safety and tolerability of DS-1205c in combination with gefitinib, the endpoints will include dose-limiting toxicities (DLTs), serious adverse events (SAEs), treatment-emergent adverse events (TEAEs), physical examination findings (including Eastern Cooperative Oncology Group [ECOG] performance status [PS]), vital sign measurements, ophthalmologic findings, standard clinical laboratory parameters, ECG parameters (including the change-from-baseline ECG parameters: HR; PR; QTcF; and QRS intervals [Δ HR, Δ PR, Δ QTcF, and Δ QRS]), echocardiogram (ECHO)/multigated acquisition (MUGA) scan findings, and radiographic findings. AEs and laboratory findings will be graded according to the National Cancer Institute-Common Terminology Criteria for Adverse Events (NCI-CTCAE) version 5.0.

Secondary Endpoints (ie, Secondary Outcome Measures)

- Cycle 0: To assess PK of DS-1205a, the endpoints will include plasma concentration of DS-1205a versus time, and Cmax, Tmax, trough plasma concentration (Ctrough), area under the plasma concentration-time curve during a dosing interval (AUCtau), and other PK parameters, as appropriate.

- Cycle 1 and beyond: To assess the PK of DS-1205a, and gefitinib, the endpoints will include plasma concentration of DS-1205a, and gefitinib versus time, and maximum observed analyte concentration during a dosing interval (Tau) (Cmax), Tmax, Ctrough, AU τ , and other PK parameters, as appropriate.
- The efficacy endpoint is ORR: the number of subjects with best objective response (complete response [CR] or PR, divided by the number of subjects in the analysis population), as determined by Investigator assessment based on RECIST version 1.1. Additional efficacy endpoints are DOR (the time from documentation of tumor response [either CR or PR] to disease progression), disease control rate (DCR) (the sum of CR rate, PR rate, and stable disease [SD] rate), PFS, time to response (TTR); and OS.

Exploratory Endpoints (ie, Exploratory Outcome Measures)

- Biomarkers measured in tumor specimens that correlate with response or toxicity to DS-1205c in combination with gefitinib (eg, AXL immunohistochemistry [IHC], AXL and AXL pathway genes measured by NanoString multiplex RNA and/or other methods, and/or protein analysis) will be assessed.

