3.2.1. Dose Escalation

3.2.1.1. Cycle 0 (Monotherapy, 7 Days)

To minimize the possibility of developing tumor flare with discontinuation of EGFR TKI, subjects who fulfill eligibility criteria will be instructed to continue their current EGFR TKI (gefitinib, erlotinib, afatinib, dacomitinib, or osimertinib) during screening. The last dose of gefitinib, erlotinib, afatinib, dacomitinib, or osimertinib must be taken 1 day before breakfast in clinic on Cycle 0, Day 1, as depicted in [Figure 3.1](#) above. This schedule provides an 8-day window between the last dose of gefitinib, erlotinib, afatinib, dacomitinib, or osimertinib, and the first dose of gefitinib.

Once eligibility is confirmed, subjects will be assigned by the Sponsor to receive DS-1205c at a specific dose level ([Table 3.1](#)). This will be either the current escalation dose (as determined by an algorithm described in detail in Section [3.2.1.2](#) below) or a previously assigned lower dose (ie, cohort backfilling).

Table 3.1: Dose Escalation Provisional Cohorts and Provisional Dosages

Cohort ^a	Cycle 0 Monotherapy (7-day cycle)	Cycle 1 and Beyond Combination Therapy (21-day cycles)	
	DS-1205c Dosage ^b	DS-1205c Dosage ^b	Gefitinib Dosage ^c
1	200 mg BID	200 mg BID	250 mg QD
2	400 mg BID	400 mg BID	250 mg QD
3	600 mg BID	600 mg BID	250 mg QD
4	800 mg BID	800 mg BID	250 mg QD

BID = twice daily; mg = milligrams; QD = once daily

- a. The second subject in each cohort should start dosing at least 24 hours after the initial dosing of the first subject. The cohort numbers in this table do not denote actual order of dose transition on the trial.
- b. Administer with a meal, with 240 mL of water. On the morning of Endpoint ECG days, breakfast should be started 30 minutes prior to dosing and should be completed within approximately 20 minutes. For all other dosings, it is recommended that meals (breakfast or dinner) be completed within approximately 30 minutes; DS-1205c should be taken immediately after meal completion. Doses of DS-1205c should be taken approximately 12 hours apart.
- c. Co-administer with morning dose of DS-1205c.

Subjects will report to the clinic on Day 1 before Cycle 0 to obtain ECGs at specified time points outlined in the Schedule of Events, Dose Escalation (Cycle 0) (see [Table 6.1](#)). These time points will be time matched to ECGs obtained on Cycle 0, Day 1.

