3.2.1.3. Dose-Limiting Toxicities (DLT)

A DLT is defined as any TEAE not attributable to disease or disease-related processes or to concomitant medications or procedures that occurs during the DLT-evaluation period (Cycle 0, Day 1 to Cycle 1, Day 21 of Dose Escalation) and is Grade 3 or above, according to NCI-CTCAE version 5.0, with the exceptions as defined below.

For hematological toxicities, a DLT is defined as follows:

Hematologic Dose-Limiting Toxicities (DLT) NCI-CTCAE version 5.0		
Hematological toxicity	NCI-CTCAE Grade	CTCAE version 5.0 Definition
Neutrophil count decreased	4 (Lasting > 7 days or neutrophil count decreased that requires supportive therapy with myeloid growth factors)	< 500/mm ³ ; < 0.5 × 10 ⁹ /L
Febrile neutropenia	≥ 3	Grade 3: ANC < 1000/mm ³ with a single temperature of > 38.3°C or a sustained temperature of ≥ 38°C for more than one hour Grade 4: Life-threatening consequences; urgent intervention indicated
Anemia	4	Life-threatening consequences; urgent intervention indicated
Platelet count decreased	≥ 3 Lasting > 7 days or with clinically significant hemorrhage	Grade 3: < 50,000 – 25,000/mm ³ ; < 50.0 – 25.0 × 10 ⁹ /L Grade 4: < 25,000/mm ³ ; < 25.0 × 10 ⁹ /L
Lymphocyte count decreased	4 Lasting ≥ 14 days	< 200/mm ³ ; < 0.2 × 10 ⁹ /L
Any	5	Death

For hepatic organ toxicities, a DLT is defined as follows:

Hepatic Dose-Limiting Toxicities (DLT) NCI-CTCAE version 5.0		
Hepatic Organ Toxicity	NCI-CTCAE Grade	CTCAE version 5.0 Definition
Serum aspartate aminotransferase (AST) increase	4	> 20.0 × the upper limit normal (ULN) if baseline was normal; > 20.0 × baseline if baseline was abnormal
Serum alanine aminotransferase (ALT) increase	4	> 20.0 × ULN if baseline was normal; > 20.0 × baseline if baseline was abnormal
AST or ALT increased	3 Lasting >5 days	> 5.0 – 20.0 × ULN if baseline was normal; > 5.0 – 20.0 × baseline if baseline was abnormal
ALT or AST increased $\geq 3.0 \times$ ULN with simultaneous TBL increased $\geq 2.0 \times$ ULN	Not applicable	Not applicable
Any	5	Death

For pulmonary toxicities, a DLT is defined as any of the following:

Pulmonary Dose-Limiting Toxicities (DLT) NCI-CTCAE version 5.0		
Pulmonary Toxicity	NCI-CTCAE Grade	CTCAE version 5.0 Definition
Confirmed interstitial lung disease (ILD)	1	Asymptomatic; clinical or diagnostic observations only; intervention not indicated
	2	Symptomatic; medical intervention indicated; limiting instrumental activities of daily living (ADL)

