Anorexia	3 That resolves to \leq grade 2 in 48 hours	Associated with significant weight loss or malnutrition (eg., inadequate oral caloric and/or fluid intake); tube feeding or TPN indicated
Isolated laboratory findings not associated with signs or symptoms, including		

 Grade 3 or 4 serum ALP increased, hyperuricemia, serum amylase increased, lipase increased, or grade 3 hyponatremia, lasting $<$ 72 hours 		
Lymphocyte count	3	$< 500 - 200/\text{mm}^3$; $< 0.5 - 0.2 \times 10^9 / \text{L}$
Subjects missing more than 25% of scheduled doses in Cycle 0 and Cycle 1 for reasons not related to AEs (eg, noncompliance) will not be evaluable for DLT.		

Management of study drug-related AEs will be as per treating physician discretion and institutional guidelines. See Section 5.5 for information regarding the use of concomitant medications.

3.2.1.3.1. TEAEs During Cycle 0

In the event of a TEAE within Cycle 0 that may delay the start of Cycle 1, Day 1, Investigators should contact the Sponsor medical monitor or designee for guidance. Investigators should refer to Section 5.4 for information on interruptions of dose.

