4.1. Inclusion Criteria

1. Male or female subjects aged 20 years and older.
2. Has histologically or cytologically documented adenocarcinoma NSCLC.
3. Has locally advanced or metastatic NSCLC, not amenable to curative surgery or radiation.
4. Has acquired resistance to EGFR TKI according to the Jackman criteria.³⁶
 - a. Historical confirmation that the tumor harbors an EGFR mutation known to be associated with EGFR TKI sensitivity (including G719X, exon 19 deletion, L858R, L861Q), OR
 - b. Has experienced clinical benefit from an EGFR TKI, followed by systemic progression of disease (RECIST version 1.1 or World Health Organization [WHO]) while on continuous treatment with an EGFR TKI.
5. Is currently receiving and able to interrupt gefitinib or discontinue erlotinib, afatinib, dacomitinib, or osimertinib.
6. Has been receiving gefitinib, erlotinib, afatinib, dacomitinib, or osimertinib for at least 6 weeks with well-controlled related toxicities less than Grade 3 in severity at the time of screening period. Subjects who have been receiving gefitinib must be taking gefitinib at a dose of 250 mg/day.
7. Has radiological documentation of disease progression while receiving continuous treatment with gefitinib, erlotinib, afatinib, dacomitinib, or osimertinib.
8. Has at least one measurable lesion per RECIST version 1.1.
9. Is willing to provide archival tumor tissue from a biopsy performed after progression during treatment with gefitinib, erlotinib, afatinib, dacomitinib, or osimertinib OR has at least one lesion, not previously irradiated, amenable to core biopsy and is willing to undergo screening tumor biopsy.
10. Demonstrates absence of EGFR T790M mutation in tumor tissue since progression during gefitinib, erlotinib, afatinib, dacomitinib, or osimertinib treatment.
11. Has ECOG PS of 0 or 1, with no deterioration over the previous 2 weeks. A table of the ECOG PS scale can be found in Appendix Section [17.4](#).
12. Has adequate bone marrow reserve and organ function, defined as:
 - a. Platelet count $\geq 100 \times 10^9/L$
 - b. Hemoglobin (Hb) $\geq 9.0 \text{ g/dL}$
 - c. Absolute neutrophil count (ANC) $\geq 1.5 \times 10^9/L$

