11.6.3. Clinical Laboratory Evaluation Analyses

Descriptive statistics will be provided for the clinical laboratory results (hematology, blood chemistry, coagulation, and urinalysis) by scheduled time of evaluation and by treatment group using the Safety Analysis Set, as well as for the change from baseline. The baseline value is defined as the last non-missing value before the initial administration of study treatment. In addition, mean change from baseline will be presented by treatment group for the maximum and minimum post-treatment values and the values at the EOT visit.

Abnormal clinical laboratory results will be graded according to NCI-CTCAE v5.0, if applicable, and the Grade will be presented in a by-subject data listing. A shift table, presenting by treatment group the two-way frequency tabulation for baseline and the worst post-treatment value according to the NCI-CTCAE Grade will be provided for clinical laboratory tests. Abnormal clinical laboratory test results deemed of clinical significance or of Grade 3 or 4 will be listed.

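### As worded, the TEAE definition in Section 11.6.1 misses a toxicity that is present at the first DS-1205c dose, clears in Cycle 0 and returns on gefitinib at a higher grade

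*Combined protocol and SAP*

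**What the plan says.** Section 11.6.1 gives three routes by which an AE becomes a TEAE during a treatment period that opens at the first dose of DS-1205c or gefitinib:

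1. It appears on treatment and was absent at pre-treatment.
2. It "reemerges during treatment, having been present at baseline, but stopped prior to treatment".
3. It "worsens in severity after starting treatment relative to the pre-treatment state, when the AE is continuous".

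The parts of the Dose Escalation design that bear on this are:

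- **Entry toxicity.** Section 4.1, criterion 6, admits subjects who have been on an EGFR TKI for at least 6 weeks "with well-controlled related toxicities less than Grade 3 in severity at the time of screening period".
- **TKI gap.** Section 3.2.1.1 has them stop that TKI before Cycle 0 and says: "This schedule provides an 8-day window between the last dose of gefitinib, erlotinib, afatinib, dacomitinib, or osimertinib, and the first dose of gefitinib". DS-1205c is given alone for the 7 days of Cycle 0, and gefitinib starts in Cycle 1 (Section 6.1.3).
- **Start of treatment.** Section 3.2.1.3.1, on Cycle 0, opens "In the event of a TEAE within Cycle 0 that may delay the start of Cycle 1, Day 1". TEAEs can therefore occur before any gefitinib is given. Section 11.1 takes baseline as the last value before the first dose of study drug.
- **Use of the term.** TEAEs are among the primary endpoints (Section 2.3.1).

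**The concern.** The design builds a stop-and-restart of EGFR inhibition into the treatment period. A skin, bowel or liver toxicity carried in from the entry TKI may ease while the TKI is withheld and come back when gefitinib is added to DS-1205c. If it comes back worse than it was at entry, a safety study of the combination should count it. Section 1.4.2 names hepatotoxicity as a risk that overlaps between the two drugs.

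Only the third route looks at grade, and it requires continuity. The second route accepts recurrence, but only if the event stopped before treatment. An event that stops in Cycle 0 falls between them. At stake is its place in the tables of TEAEs, treatment-emergent SAEs and drug-related events in Section 11.6.1. Any such omission lowers the counts and cannot raise them.

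**Working it through.** The plan gives no figure to reproduce, and no rate can be computed. The check is logical: apply the three routes to a set of event histories, with treatment starting at the first DS-1205c dose on Cycle 0, Day 1.

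| History | Route 1: absent before | Route 2: stopped before treatment, returned | Route 3: worse and continuous | TEAE as written | TEAE if continuity is dropped |
|---|---|---|---|---|---|
| New onset at Grade 2 | yes | no | no | yes | yes |
| Grade 1, stopped before Cycle 0 Day 1, returns at Grade 2 | no | yes | no | yes | yes |
| Grade 1 at first dose, continuous, rises to Grade 2 | no | no | yes | yes | yes |
| Grade 1 at first dose, clears in Cycle 0, returns at Grade 2 | no | no | no | **no** | yes |
| Grade 2 at first dose, clears in Cycle 0, returns at Grade 3 | no | no | no | **no** | yes |
| Grade 1 at first dose, clears in Cycle 0, returns at Grade 1 | no | no | no | no | no |

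The fourth and fifth rows are the gap. Each fails route 1 because the toxicity was present at pre-treatment, route 2 because it stopped during treatment, and route 3 because it was interrupted.

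Route 2 has no grade condition. So a toxicity that stops just before the first dose and returns at its old grade counts, while one that stops just after the first dose and returns at a higher grade does not.

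Two readings might close the gap:

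- **Treatment means gefitinib.** Route 2 would then apply. Section 3.2.1.3.1 rules this out by recognising TEAEs in Cycle 0, and the baseline rule in Section 11.1 also runs from the first dose of study drug.
- **Each return is a new AE, absent at pre-treatment.** Route 1 would then apply. But if every recurrence were a new AE, route 2 would have nothing left to do. Its presence shows that the definition treats a recurrence as the same AE.

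Section 11.6.3 gives a useful contrast. Its laboratory shift table is "the two-way frequency tabulation for baseline and the worst post-treatment value according to the NCI-CTCAE Grade", with no continuity condition. The two outputs need not agree, because under Section 9.1 not every laboratory abnormality is an AE. The contrast shows only that the plan elsewhere measures worsening directly against baseline.

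**The case against.** The strongest reply is that the gap depends on an unstated unit of analysis. Section 9.4.3 reports severity by episode, and Section 9.1 sends conditions known before consent to medical history. A return after full clearance could then be entered as a new AE with on-treatment onset and be counted under route 1. This stands in part: a programmer working by episode might count the event. Section 11.6.1 does not say so, however, and its second route points the other way, so two careful programmers could classify the same event differently.

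Second, Section 11.10 leaves safety definitions to the SAP, and no separate SAP text was available for this check. It may refine the rule. But Section 11.6.1 already states a definition, and a SAP that repeats it would carry the same gap.

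Third, the history is narrow. The toxicity must last to the first DS-1205c dose, clear completely, return and exceed its earlier grade. Partial improvement leaves it continuous, and route 3 then works. The events also stay visible: all AEs are listed by subject (Section 11.6.1), laboratory changes appear in the shift tables (Section 11.6.3), and physical-examination findings are listed (Section 11.6.5). All of this stands and limits the weight of the point.

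A reader might go further and infer that DLTs are lost, since Section 3.2.1.3 says "A DLT is defined as any TEAE not attributable to disease or disease-related processes or to concomitant medications or procedures". The documents do not support that. Investigators are told to judge AEs and SAEs for DLT (for example Section 6.1.2.2) and to report DLTs as they occur (Section 3.2.1.4), so such an event would probably still be raised. Nor do Sections 6.1.2.2 and 3.2.1.3 conflict: the first refers to the second for its definition.

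**Conclusion.** The definition is wrong as written, and the point is minor. It does not capture an AE that is present at the first DS-1205c dose, resolves in the EGFR-TKI-free Cycle 0 and recurs on gefitinib above its pre-treatment grade. The consequence is a possible undercount in the tables of TEAEs, treatment-emergent SAEs and related events.

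No numerical size is given, because the documents do not say how often entry toxicities follow this course; the frequency is probably small. Counting possible grade pairs, or working out what one subject is worth in a small cohort, would not measure it.

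The conclusion rests on three assumptions: treatment starts at the first DS-1205c dose, a recurrence is the same AE (as route 2 implies), and the SAP does not refine the rule. Returns at or below the pre-treatment grade are a matter of convention and are not part of the finding.

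**What to change.** In Section 11.6.1, replace the continuity condition at the end of the third route with: whether or not the AE was continuous. Use the same wording in the SAP. The two missed histories in the table then qualify, and a return at the pre-treatment grade still does not. No separate DLT sentence is needed, because Section 3.2.1.3 defines a DLT through the TEAE and inherits the correction.

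The cost is one clause in each document, with no new visit or sample. Changing the protocol text means an amendment with review and approval under Section 15.7. The pre-treatment grade of ongoing TKI toxicities must be on record, including those held as medical history under Section 9.1. The third route already needs that grade, so this is not a new demand, but the text does not say that medical history captures it and this should be checked.

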11.6.2. Electrocardiogram Analyses

Electrocardiogram parameters (PR, RR, QRS, QT, and QTcF) will be summarized using descriptive statistics for actual values and for changes from baseline by scheduled time of evaluation, including the EOT visit and the maximum post-treatment value. The corrected QT intervals using Fridericia's formula will be calculated as follows: $QTcF = QT/(RR)^{1/3}$.

The incidence of notable ECG changes in maximum absolute QT and QTcF intervals over all post-treatment evaluations, as well as in QT and QTcF maximum changes from baseline over all post-treatment evaluations will be summarized. A listing of ECG data will be provided.

The Concentration-QTc analysis plan will be presented in a separate document.

11.6.3. Clinical Laboratory Evaluation Analyses

Descriptive statistics will be provided for the clinical laboratory results (hematology, blood chemistry, coagulation, and urinalysis) by scheduled time of evaluation and by treatment group using the Safety Analysis Set, as well as for the change from baseline. The baseline value is defined as the last non-missing value before the initial administration of study treatment. In addition, mean change from baseline will be presented by treatment group for the maximum and minimum post-treatment values and the values at the EOT visit.

Abnormal clinical laboratory results will be graded according to NCI-CTCAE v5.0, if applicable, and the Grade will be presented in a by-subject data listing. A shift table, presenting by treatment group the two-way frequency tabulation for baseline and the worst post-treatment value according to the NCI-CTCAE Grade will be provided for clinical laboratory tests. Abnormal clinical laboratory test results deemed of clinical significance or of Grade 3 or 4 will be listed.

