- d. Prothrombin time and activated partial thromboplastin time (aPTT) $\leq 1.5 \times$ the upper limit normal (ULN), except for patients on coumarin-derivative anticoagulants or other similar anticoagulant therapy, who must have prothrombin time-International Normalized Ratio (PT-INR) within therapeutic range as deemed appropriate by the Investigator.
- e. Serum creatinine $\leq 1.5 \times$ ULN, or creatinine clearance ≥ 50 mL/min as calculated using the Cockcroft-Gault equation (Section 17.1); confirmation of creatinine clearance is only required when creatinine is $> 1.5 \times$ ULN.
- f. AST/ALT $\leq 3.0 \times$ ULN (if liver metastases are present, $\leq 5.0 \times$ ULN).
- g. Total bilirubin $\leq 1.5 \times$ ULN if no liver metastases or $< 3.0 \times$ ULN in the presence of documented Gilbert's Syndrome (unconjugated hyperbilirubinemia) or liver metastases.
- h. CK $< 1.5 \times$ ULN.
- i. Lipase $< 2 \times$ ULN.

13. Has adequate treatment washout period before first dose of study drug, defined as:

- a. QTc prolonging medications ≥ 10 days (Section 17.6)
- b. CYP3A4 strong inducers ≥ 10 days (Section 17.6)
- c. Proton pump inhibitors (eg, omeprazole, esomeprazole, lansoprazole, dexlansoprazole, and pantoprazole) ≥ 5 days

14. Female subjects of reproductive/childbearing potential with a male sexual partner must agree to use a highly effective form of contraception or avoid intercourse during and upon completion of the study and for at least 3 months after the last dose of study drug. For the purpose of this protocol, methods considered as highly effective birth control include:

- a. Combined (estrogen- and progestogen-containing) hormonal contraception associated with inhibition of ovulation (oral, intravaginal, or transdermal delivery). *
- b. Progestogen-only hormonal contraception associated with inhibition of ovulation (oral, injectable, or implantable delivery). *
- c. Intrauterine device (IUD).
- d. Intrauterine hormone-releasing system (IUS).
- e. Bilateral tubal occlusion.
- f. Vasectomized partner.
- g. Complete sexual abstinence.

Non-child-bearing potential is defined as pre-menopausal with documented tubal ligation or hysterectomy; OR postmenopausal with documented ≥ 12 months of spontaneous amenorrhea (in questionable cases, a blood sample with simultaneous follicle-stimulating hormone [FSH] > 40 mIU/mL and estradiol < 40 pg/mL [< 147 pmol/L] is confirmatory).

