Creatinine increased	Grade 3 ($> 3.0 \times$ baseline; $> 3.0 - 6.0 \times$ ULN)	
Delay dose until resolved to \leq Grade 2 ($> 1.5 - 3.0 \times$ ULN; $> 1.5 - 3.0 \times$ baseline), then:
 
 • If resolved in \leq 7 days, resume study medications. • If resolved in $>$ 7 days and \leq 21 days, study medications may be resumed after discussion and agreement between the Investigator and Sponsor. 
If not resolved in $>$ 21 days, discontinue subject from treatment.

	Grade 4 ($> 6.0 \times$ ULN)	
Discontinue subject from study treatment.

Table 5.1: Dose Interruption and Dose Resumption Criteria (Continued)

	Worst toxicity NCI-CTCAE v5.0 Grade (unless otherwise specified) by Definition	Schedule modification for DS-1205c and gefitinib
Hepatobiliary disorders		
AST or ALT increased	Grade 2 ($> 3.0 - 5.0 \times \text{ULN}$ if baseline was normal; $> 3.0 - 5.0 \times \text{baseline}$ if baseline was abnormal)	
If simultaneous TBL increased $\geq 2.0 \times \text{ULN}$, then see “AST or ALT increased with simultaneous TBL increased” below. Otherwise:
 
 Continue study medications. Monitor AST/ALT 48 to 72 hours later, and continue regular monitoring until resolution.
	Grade 3 ($> 5.0 - 20.0 \times \text{ULN}$ if baseline was normal; $> 5.0 - 20.0 \times \text{baseline}$ if baseline was abnormal)	
If simultaneous TBL increased $\geq 2.0 \times \text{ULN}$, then see “AST or ALT increased with simultaneous TBL increased” below.
 
Otherwise:
 
Delay study medications until resolved to \leq Grade 2.
 
Monitor AST/ALT 48 to 72 hours later, and continue regular monitoring until resolved to \leq Grade 2.
 
 If resolved in ≤ 7 days, resume study medications. If resolved in > 7 days and ≤ 21 days, study medications may be resumed after discussion and agreement between the Investigator and Sponsor. If not resolved in > 21 days, discontinue subject from treatment.

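### The laboratory shift table grades AST, ALT and bilirubin on a scale that changes reference when baseline is abnormal, so liver worsening can be masked or, for the higher eligible baselines, shown as improvement

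*Combined protocol and SAP*

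**What the plan says.** Section 11.6.3 sets the scale: "Abnormal clinical laboratory results will be graded according to NCI-CTCAE v5.0, if applicable". It then plans, for the laboratory tests: "A shift table, presenting by treatment group the two-way frequency tabulation for baseline and the worst post-treatment value according to the NCI-CTCAE Grade". On baseline it says: "The baseline value is defined as the last non-missing value before the initial administration of study treatment". It does not say which reference is used to grade that baseline value, or that both axes share one.

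The grades themselves are printed elsewhere in the protocol. The hepatic DLT table in Section 3.2.1.3 gives Grade 3 for AST or ALT as "> 5.0 – 20.0 × ULN if baseline was normal; > 5.0 – 20.0 × baseline if baseline was abnormal" and Grade 4 for AST as "> 20.0 × the upper limit normal (ULN) if baseline was normal; > 20.0 × baseline if baseline was abnormal"; the ALT Grade 4 row has the same structure. Table 5.1 in Section 5.4.1 prints Grade 2 for AST/ALT and Grades 2 to 4 for TBL with the same two references.

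Abnormal baselines are eligible under Section 4.1. Criterion 12f allows AST/ALT up to 3.0 × ULN, raised to 5.0 × ULN "if liver metastases are present". Criterion 12g allows TBL up to 1.5 × ULN, or below 3.0 × ULN with Gilbert's syndrome or liver metastases.

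Section 11.6.3 also plans a by-subject listing that shows the grade, a listing of results that are clinically significant or Grade 3 or 4, and change-from-baseline summaries that include the maximum post-treatment value.

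**The concern.** A shift table is informative only if both axes measure the same thing. Here a subject with an abnormal baseline is graded after treatment against that baseline, so the post-treatment axis is not the ULN axis. The baseline cell can be filled in two ways consistent with the text, and neither works. Graded on ULN, the baseline sits on a different scale from the worst value. Graded against itself, its ratio is always 1, so every abnormal baseline drops to the bottom row.

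Safety is part of the primary objective of Dose Escalation (Section 2.1.1), and Section 1.4.2 names hepatotoxicity as a risk that DS-1205c and gefitinib share. A liver table that can show a large rise as no change, or as a lower grade, is a weak basis for describing that risk.

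**Working it through.** The plan states no figure of its own on this point, so there is none to reproduce. The check applies the printed cut-offs to eligible baselines.

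**Inputs**
- b = baseline and w = worst post-treatment value, both in multiples of ULN; r = w / b.
- AST/ALT: Grade 2 >3–5, Grade 3 >5–20, Grade 4 >20 (Sections 3.2.1.3 and 5.4.1).
- TBL: Grade 2 >1.5–3, Grade 3 >3–10, Grade 4 >10 (Section 5.4.1, Table 5.1).
- Reference: ULN if baseline was normal, baseline if it was abnormal.
- Range of b: the limits in criteria 12f and 12g, taken to hold at baseline.
- Grade 1 cut-offs are not printed, so lower values are shown only as below 2.

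**Readings**
- Reading 1: baseline graded on b, worst value on r.
- Reading 2: baseline graded on b / b = 1, worst value on r.
- Comparator: both graded on ULN, that is on b and w.

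| Test | b → w | r | Reading 1 | Reading 2 | Both on ULN |
|---|---|---|---|---|---|
| ALT | 4.5 → 13 | 13/4.5 = 2.89 | 2 → below 2 | below 2 → below 2 | 2 → 3 |
| ALT | 5 → 15 | 15/5 = 3.00 | 2 → below 2 | below 2 → below 2 | 2 → 3 |
| ALT | 5 → 22.5 | 22.5/5 = 4.50 | 2 → 2 | below 2 → 2 | 2 → 4 |
| ALT | 2.5 → 7.4 | 7.4/2.5 = 2.96 | below 2 → below 2 | below 2 → below 2 | below 2 → 3 |
| TBL | 2.8 → 4.0 | 4.0/2.8 = 1.43 | 2 → below 2 | below 2 → below 2 | 2 → 3 |
| TBL | 2.0 → 3.0 | 3.0/2.0 = 1.50 | 2 → below 2 | below 2 → below 2 | 2 → 2 |

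**Where reversal occurs (Reading 1)**
- AST/ALT: baseline is Grade 2 on ULN when 3 < b ≤ 5, which needs liver metastases. Any rise with w ≤ 3b then falls below Grade 2. At b = 5 that covers rises up to 3 × 5 = 15 × ULN.
- TBL: baseline is Grade 2 on ULN when 1.5 < b < 3, which needs Gilbert's syndrome or liver metastases. Any rise with w ≤ 1.5b falls below Grade 2. It is also Grade 3 on ULN only if w > 3, so b must exceed 3/1.5 = 2.

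**Where masking occurs**
- An AST/ALT value is Grade 3 on ULN but below Grade 2 as printed when 5 < w ≤ 3b. This needs b > 5/3 = 1.67, so it includes subjects without liver metastases.
- Under Reading 2 nothing reverses, but the 4.5 → 13 and 2.8 → 4.0 cases still show no shift.

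**Effect on the Grade 3/4 listing**
- AST/ALT reaches Grade 3 only when w > 5b: above 12.5 × ULN at b = 2.5, 22.5 at b = 4.5 and 25 at b = 5.
- TBL reaches Grade 3 only when w > 3b: above 8.4 × ULN at b = 2.8.

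**The case against.** The strongest reply has four parts.

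1. **Other outputs carry the information.** Section 11.6.3 plans a by-subject listing of graded results and change-from-baseline summaries that do not depend on grade. Section 9.8 requires the investigator to assess every laboratory value for clinical significance. Section 9.3.1 requires reporting of potential Hy's Law cases on ULN multiples whatever the baseline. This largely stands: a reader might infer that these rises would vanish from the report, and the documents do not support that. The offset is partial, though. The by-subject listing shows the same grade, a mean change does not identify the subject, and the Hy's Law rule needs aminotransferase and bilirubin elevations together, so it misses an isolated ALT rise.

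2. **Reversal needs a convention the plan does not state.** This is true, and the SAP (Sections 11.1 and 11.10) may still settle it before database lock. But the alternative, grading baseline against itself, hides the same rises. Leaving the choice open is therefore not harmless.

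3. **The affected group is narrow.** This stands for reversal, which cannot be assumed for every abnormal baseline. The 2.5 to 7.4 × ULN case is masking only.

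4. **Nothing decisive rests on the table.** This stands. Section 11.6 calls the safety analyses descriptive in general, escalation runs on DLTs through the Bayesian model, and nothing ranks this table above the other laboratory outputs.

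A reader might also turn the 11.4% ALT-increase rate in Section 1.4.2 into an expected number of affected subjects. That rate describes patients who received gefitinib in trials. It is not a baseline rate, and the documents give none. Nor do they support describing the affected subjects as those with the poorest liver function, since Gilbert's syndrome is one route in. ALP cannot be included, because its grade definitions are not printed.

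**Conclusion.** The point holds as a defect in one descriptive safety table and in the grade-based part of one listing. As written, the table gives a misleading picture for AST, ALT and TBL in subjects with abnormal baselines under either way of grading the baseline value. It reverses worsening if baseline is graded on ULN and falls in the Grade 2 ranges derived above, and otherwise it can mask it. In the cases shown the distortion is one or two grades: ALT from 4.5 to 13 × ULN appears as a fall from Grade 2 instead of a rise to Grade 3, and ALT from 2.5 to 7.4 × ULN appears as no shift instead of a rise to Grade 3.

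This rests on the cut-offs as printed in the protocol, on baselines within the entry limits, and on the combined document containing no further rule for grading baseline. How many subjects would be affected cannot be estimated from the documents. With about 18 subjects planned for Dose Escalation, a single misplaced subject would be noticeable. The change should be made while the SAP is open. It does not bear on dose decisions.

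**What to change.** In Section 11.6.3 or the SAP:

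- Build the AST, ALT and TBL shift tables on fixed ULN multiples for both the baseline and the worst post-treatment value. For AST/ALT use ≤1, >1–3, >3–5, >5–20 and >20 × ULN. For TBL use ≤1, >1–1.5, >1.5–3, >3–10 and >10 × ULN. With one scale on both axes, a rising value cannot move to a lower category.
- Add to the Grade 3/4 listing every AST or ALT value above 5 × ULN and every TBL value above 3 × ULN. No result now listed is lost. For a normal baseline the Grade 3 thresholds are the same, and for a baseline above ULN any value over 5 × baseline (or 3 × baseline for TBL) also exceeds 5 × ULN (or 3 × ULN).
- Keep v5.0 grades for adverse event reporting, and leave the DLT and dosing criteria unchanged.

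The cost is a few lines of text and one extra table programme, with no new data. The liver table may look slightly less favourable than it would on v5.0 grades.
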